Telephone assessment				X	X	
HIV RNA, Plasma	X	X	X			X
CD4+ T-cell count	X		X			X
Drug resistance testing	X					
HIV RNA, CSF		X	X			X
HIV Dementia Scale		X				X
Study drug dispensing		X	X	X	X	X
Safety assessment			X			X
PK assessment			X			X

Signs and symptoms, laboratory results, and toxicities \geq Grade 2 will be recorded on the appropriate case report forms (CRFs).

Screening and Entry Evaluations

1) Screening Evaluations will occur within 28 days of study entry

- a) Details of the study will be carefully discussed with subjects during screening and the subject asked to read and sign an informed consent approved by the IRB at the participating institutions.
- b) Documented presence of HIV infection, as specified in Section 3.1.1 of the master protocol, prior to study entry.
- c) A brief medical history will be obtained and will include:
 - i) Previous diagnoses including liver disease, renal disease, fracture, osteoporosis, allergies, drug reactions, and most recent menses.
 - ii) Current prescription and non-prescription medications taken within 14 days prior to entry.
 - iii) Recent use of drugs of abuse or unprotected sexual contacts. Past use of needles.
 - iv) A signs-and-symptoms assessment, including: vital signs, height, and weight. Vital signs will include temperature, blood pressure, and pulse rate.

- d) 35 mL of blood and 15 mL of urine will be collected using standard methods.
- 2) The following laboratory tests must be performed within 28 days prior to study entry, unless otherwise noted:
- a) Hematology: hemoglobin, hematocrit, mean corpuscular volume (MCV), white blood cell count, differential white blood cell count, and platelet count.
- b) Blood chemistries: electrolytes, blood urea nitrogen (BUN), creatinine, glucose, phosphorus, and calcium.
- c) Liver function tests: total bilirubin, AST, ALT, alkaline phosphatase, and albumin.
- d) Coagulation: prothrombin time, international normalized ratio, partial thromboplastin time
- e) Urinalysis, including urine glucose and protein
- f) Estimated glomerular filtration rate (eGFR)
- g) For women of childbearing potential: Serum or urine pregnancy test.
- h) HIV RNA in blood plasma
- i) Lymphocyte subsets in blood (including CD4+ and CD8+ T-cell absolute counts and percentages)
- j) Hepatitis C and hepatitis B serologic testing
- k) Rapid plasmin reagent (RPR)
- 1) Drug resistance mutation genotyping in blood
- m) 5 mL of blood plasma will be stored at -80C.

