a) STRIBILD is NOT recommended for coadministration with: emtricitabine or tenofovir DF (ATRIPLA, COMPLERA, EMTRIVA, TRUVADA, VIREAD); products containing lamivudine (COMBIVIR, EPIVIR, EPIVIR-HBV, EPZICOM, TRIZIVIR) or adefovir dipivoxil (HEPSERA); or ritonavir (NORVIR, KALETRA).

Contraindications

a) Coadministration of STRIBILD is contraindicated with drugs that are highly dependent on CYP3A for clearance and for which elevated plasma concentrations are associated with serious and/or life-threatening events, *e.g.* alfuzosin, rifampin, ergo derivatives, cisapride, St. John's wort, lovastatin, simvastatin, sildenafil, triazolam, oral midazolam. Specific case-by-case exemptions may be considered by the study investigators.

Management of Selected Toxicities

New Onset or Worsening Renal Impairment

a) Renal impairment, including acute renal failure and Fanconi syndrome, has been reported with the use of STRIBILDTM. If renal impairment occurs as indicated by a decrease of estimated creatinine clearance below 50 mL/min, study treatment will be discontinued. Subjects will be followed off treatment with evaluations as per section 4.2 of the master protocol.

Lactic Acidosis/Severe Hepatomegaly with Steatosis

a) Lactic acidosis and severe hepatomegaly with steatosis, including fatal cases, have been reported with the use of tenofovir DF, a component of STRIBILD, in combination with other antiretrovirals. Treatment with STRIBILD should be suspended in any subject who develops clinical or laboratory findings suggestive of lactic acidosis or pronounced hepatotoxicity.

Bone Effects, Fat Redistribution, and Immune Reconstitution Syndrome

- a) Decreases in bone mineral density, redistribution/accumulation of body fat, and immune reconstitution syndrome have been reported in patients treated with STRIBILDTM, which may necessitate further evaluation and treatment.
- b) Any Grade 2 or higher symptoms or laboratory abnormalities will result in termination of the subject from the study (see Section 4.2 of the master protocol for post-treatment evaluations).
- c) If a subject discontinues the study drugs prior to the pharmacokinetic sampling on day 14, s/he will be replaced in the original sample size.

Criteria for Treatment Discontinuation

- a) The subject or legal guardian refuses further treatment and/or follow-up evaluations.
- b) The investigator determines that further participation would be detrimental to the subject's health.

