Occasionally (about 5 in 100 times), participants may experience leaking of cerebrospinal fluid into the tissues of back after the procedure which is known as post-LP headaches. The headache is not dangerous, but can be uncomfortable. You will be given instructions on how to contact the on-call research clinician (7 days a week, 24 hours a day) if you experience this type of headache. Rarely (about 1 in 100 times) the headache pain may be severe and persistent enough to require an epidural blood patch. A blood patch is a procedure in which 1-3 teaspoons of blood is drawn from your arm and injected into your lower back. Your blood clots there to stop the fluid leakage that is causing the headache. The blood patch is performed by an anesthesiologist physician at the hospital.

Reporting Requirements:

If a subject is tested for Hepatitis B and C, there may be a chance they will be diagnosed with one of these infections. The study staff will talk with them about their options and provide them with referrals of doctors and/or facilities that can provide treatment for their hepatitis infection if they are found to have one of these infections.

Efforts will be made to keep their personal information confidential, however, all cases Hepatitis B or C must be reported to the public health department. According to California state law, study staff is required to report their name, contact information and treatment records if their tests show evidence of active Hepatitis B or C.

Risk of Blood Draws

Risks include pain, bruising, fainting, swelling, dizziness or possible infection at the blood withdrawal sites (rare).

Risks of Stribild

Common adverse drug reactions in clinical studies (incidence ≥5%; all grades) nausea (16%), diarrhea (12%), abnormal dreams (9%), headache (7%), fatigue (4%), rash (3%), insomnia (3%), and dizziness (3%). Laboratory abnormalities can also occur including elevations in creatine kinase (7%), elevated amylase (3%), and hematuria (3%). Serious adverse events, including lactic acidosis and severe hepatomegaly, have been reported but are uncommon.

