15. RISK MANAGEMENT PROCEDURES AND ADEQUACY OF RESOURCES

We will implement the following procedures to safeguard the patients against risk. In order to maintain subject confidentiality all laboratory specimens, evaluation forms, reports, and other records will be identified by a coded number only. All records will be kept in a locked file cabinet. Any information obtained as part of this study will not be released without written permission of the subject, except as necessary for monitoring by the UCSD IRB or for monitoring by the FDA. Please see the data security plan in section 16 for more information.

Experienced phlebotomists will obtain blood specimens.

Risks and reported adverse events of Stribild will be clearly explained to each subject during the informed consent process. At each study visit the study nurses will ask participants to report any symptoms they experience while taking Stribild. During PK visits, a temporary intravenous catheter will be placed in the subject's arm to facilitate multiple blood draws and minimize pain and swelling associated with repeated venipuncture. The intravenous catheter will be removed at the end of the 6-hour blood collection. Participants will be instructed to contact the Clinical Trials Unit in the event of adverse events by telephone 24 hours a day/7 days a week. Following a telephone interview, the Clinical Trials Unit will schedule a visit for an additional assessment as necessary. For serious adverse events participants, will be instructed to immediately discontinue Stribild and to go the closest emergency room. Any Grade 3 or higher symptoms or laboratory abnormalities will result in termination of Stribild. Subjects who experience renal function abnormalities with

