estimated creatinine clearance below 50 ml/min will also have the study drug terminated and complete the evaluations listed in Section 4.2. Subjects will also have the study drug terminated in cases of suspected drug-related toxicity, taking prohibited concomitant medications (see section 4.2 of the master protocol), if a female subject is pregnant or breast-feeding, if the subject is judged by the investigators to be at significant risk of failing to comply with the provisions of the protocol as to cause harm to self or seriously interfere with the validity of the study results, at the discretion of the investigator, institutional review board (IRB), Food and Drug Administration, pharmaceutical sponsor; or if the subject requests to withdraw from the study. In case of injury or serious adverse events, the investigators will assist the subject in obtaining appropriate medical treatment.

Lumbar Punctures: Experienced research clinicians (either a physician or a nurse) will perform all lumbar punctures. Local back pain will be minimized by injection of an anesthetic, 1% lidocaine into the subcutaneous tissue surrounding the needle puncture site. Oral analgesics and anti-inflammatory medications will be provided when necessary. Following LP, patients will be observed for 10-15 minutes. Over 3,000 LPs have been performed at the HNRC using non-cutting or "pencil point" spinal needles that reduce the risk of post-LP cephalgia. A site clinician will be available by pager 24 hours-per-day to respond to problems, should they occur. If post-LP headache occurs, initial conservative management will include recumbency, hydration, and oral analgesics. When headaches are prolonged, a blood patch, involving an epidural injection of a sample of the subject's own blood, may be performed by consulting anesthesiologists.

UCSD AVRC will serve as the lead/coordinating site for this study. Clinics at the Erie County Medical Center and University of Rochester will be subordinate sites, as outlined in the master protocol team roster. All adverse events, protocol deviations, and other study related reports will be reviewed by the PI as outlined in section 5.0 of the Master Protocol. All data transfers and other study related information will be performed in accordance with the Data Security Plan.

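### Section 9 ends participation at any Grade 2 or higher event, Section 15 stops Stribild only at Grade 3 or higher, and the supplied text does not say which governs

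*Combined protocol and SAP*

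**What the plan says.** The plan sets grade-based stopping in two places.

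- **Section 9, Management of Selected Toxicities**, item b under the bone, fat redistribution and immune reconstitution subheading: "Any Grade 2 or higher symptoms or laboratory abnormalities will result in termination of the subject from the study".
- **Section 15, Risk Management Procedures**: "Any Grade 3 or higher symptoms or laboratory abnormalities will result in termination of Stribild".

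Section 15 adds two triggers that carry no grade. One is "Subjects will also have the study drug terminated in cases of suspected drug-related toxicity". The other allows drug to be stopped "at the discretion of the investigator, institutional review board (IRB), Food and Drug Administration, pharmaceutical sponsor".

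On lumbar puncture, Section 14 gives the frequency of leakage headache: "Occasionally (about 5 in 100 times), participants may experience leaking of cerebrospinal fluid". It adds: "Rarely (about 1 in 100 times) the headache pain may be severe and persistent enough to require an epidural blood patch". Section 15 sets out the handling: "If post-LP headache occurs, initial conservative management will include recumbency, hydration, and oral analgesics", with a blood patch possible for prolonged headache. That paragraph does not mention stopping drug or leaving the study.

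Other parts of Section 9 fix the consequences of an early stop. The premature discontinuation visit has no lumbar puncture, no PK assessment and no drug dispensing. A subject is replaced only if lost before the first on-treatment PK assessment. The criteria for treatment discontinuation refer to Section 6.6 of the master protocol for drug toxicity. That document was not among those supplied.

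**The concern.** The two sentences are near copies with different grades and different actions. A subject with a Grade 2 event must leave the study under Section 9. Under Section 15 the grade alone does not stop the drug. Applying the Section 9 rule everywhere would breach neither sentence, but it would leave the Section 15 grade trigger with nothing to do, and a site working from Section 15 is not told to act at Grade 2.

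Two things are at stake. First, this is a mandatory stopping rule in a three-site study, and whether a subject stays on treatment could depend on which section is followed. Second, the rule affects the data. Section 9 plans a within-subject analysis of week 2 against week 24, and a subject removed between those visits contributes only the week 2 sample. Toxicities are recorded on the CRFs from Grade 2 upward, so the events in question will be seen.

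**Working it through.** **Step 1. The rules side by side.**

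| Event | Section 9, item b | Section 15 |
|---|---|---|
| Grade 3 or higher, any cause | Leaves study | Stribild stopped |
| Grade 2, suspected drug-related | Leaves study | Stribild stopped (ungraded toxicity clause) |
| Grade 2, not attributed to drug | Leaves study | No stop on grade; discretion only |

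Only the last row diverges on whether treatment must end. The actions also differ in words (study versus drug). In practice, leaving the study ends study treatment: item b points to post-treatment evaluations, and the discontinuation visit dispenses no drug.

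**Step 2. Consequence for the samples.** A subject in the last row, after day 14, keeps the week 2 pair under either rule. Under Section 9 the week 24 pair is lost and the subject is not replaced. Under Section 15 the grade alone costs nothing.

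**Step 3. Illustration from the plan's own figures.** Only the week 2 puncture matters here: subjects lost before day 14 are replaced, and the week 24 puncture comes after the last PK sample. The inputs are 14 subjects, headache in about 5 per 100 punctures, and headache severe enough for a blood patch in about 1 per 100. Assume the severe ones are Grade 3 or higher and the rest are not attributed to drug. Grade 2 headaches are then at most 0.05 − 0.01 = 0.04 per puncture.

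| Share of non-severe headaches that are Grade 2 | p | Expected subjects, 14 × p | Chance of at least one, 1 − (1 − p)^14 |
|---|---|---|---|
| All (upper bound) | 0.04 | 0.56 | 1 − 0.96^14 = 0.435 |
| Half | 0.02 | 0.28 | 1 − 0.98^14 = 0.246 |
| A quarter | 0.01 | 0.14 | 1 − 0.99^14 = 0.131 |

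**Step 4. All Grade 2 events not attributed to drug, after day 14.** The documents give no rate, so the per-subject values of p below are assumptions. Two PK visits in 14 subjects give 14 × 2 = 28 possible pairs. The plan's target is 22, so 28 − 22 = 6 pairs can be lost. With losses Binomial(14, p) and no other losses:

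| Assumed p | Expected lost week 24 pairs | Chance of at least one | Chance of more than six (below 22 pairs) |
|---|---|---|---|
| 0.05 | 0.7 | 0.512 | 0.000002 |
| 0.10 | 1.4 | 0.771 | 0.0002 |
| 0.20 | 2.8 | 0.956 | 0.0116 |
| 0.30 | 4.2 | 0.993 | 0.0933 |

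The conclusion does not depend on the plan's power calculation.

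**The case against.** **Subheading.** The strongest objection is scope. Each subheading in this part of Section 9 names effects and then an action, so item b may be the action for bone, fat and immune reconstitution effects only. A stricter rule for named effects can sit beside a general Grade 3 rule, as the separate renal rule does. This reading is possible. Against it, the sentence covers any symptom or laboratory abnormality, and the next item under the same subheading is a study-wide replacement rule. On the narrow reading the thresholds still differ for those effects, and nothing says that the stricter one is meant as an exception.

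**Master protocol.** The supplied text is one institution's application and defers to master protocol Sections 4.2 and 6.6, which may be what sites apply. That limits certainty about what happens in practice. It does not remove the two different grades from this document.

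**Existing safeguards.** Drug-attributed Grade 2 events can end treatment under both sections, and investigator discretion exists in both. This stands, and it narrows the point to events not attributed to drug. Discretion does not reconcile two mandatory thresholds.

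**The headache example.** The management paragraph in Section 15 mentions no stopping at any severity, so its silence cannot separate Grade 2 from Grade 3. Headache is also a listed Stribild reaction (7%), so attribution may be uncertain. Both remarks are fair. The example rests on the triggers themselves: a Grade 2 headache caused by the puncture meets the Section 9 rule as worded and does not meet the Section 15 grade rule.

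**The rates.** The 44% needs every non-severe headache to be Grade 2 and none to be suspected as drug-related, and the 5% to 30% rates have no source in the documents. They show scale only.

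**Conclusion.** The concern holds. The plan carries two mandatory thresholds for stopping on grade, and the supplied text does not say which governs. Confidence in that mismatch is high. How it would play out at sites depends partly on the unseen master protocol.

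The divergence is mainly over Grade 2 events not attributed to drug. At Grade 3 and above both sections act, so no gap is claimed there. On the headache illustration the effect is at most 0.56 subjects in 14, with a 44% chance of at least one, or 25% and 13% on the smaller assumed shares. Across the assumed rates for all such events, 0.7 to 4.2 week 24 pairs would be lost, with at most a 9.3% chance of falling below 22 pairs. No shortfall against that target is shown.

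The point must still be fixed, because it is a subject-level stopping rule that also affects who reaches the week 24 PK assessment.

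**What to change.** Reconcile item b in Section 9 with the Grade 3 sentence and the ungraded toxicity clause in Section 15. State one threshold and one action, in the same words in both sections and consistent with master protocol Section 6.6. Say explicitly how the rule treats events not attributed to drug, with headache after lumbar puncture as a named case. If item b is meant only for the effects in its subheading, say so there.

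The choice of threshold and action belongs to the investigators and sponsor; none is proposed here. The safety monitor's report needs no change, since the Safety Monitoring Plan in Section 15 already lists drug discontinuations with their reasons. The cost is protocol wording, with no added visits or patients.

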10. HUMAN SUBJECTS

HIV-1 infected subjects will be recruited via IRB-approved posters and flyers and advertisements in local publications. All necessary precautions will be taken to ensure participant confidentiality. Participants will be informed in the informed consent document that their participation will be confidential and their information

will be protected.

Inclusion Criteria

- Adult men or women aged 18-60 years. Able and willing to provide informed consent.
- Presence of HIV-1 infection as documented by a licensed ELISA test kit and confirmed by Western blot or HIV RNA.
- Naive to EVG
- Screening plasma HIV-1 RNA \geq 5,000c/ml and CD4+ T-cell count \geq 200cells/mm³.

Exclusion Criteria

- Presence of primary drug resistance mutations for EVG, tenofovir, or emtricitabine.
- Use of drugs of abuse or alcohol which would interfere with adherence or completion of this study. While on-study, subjects will be instructed not to consume alcohol for 48 hours prior to PK sampling days.
- Pregnancy or breast-feeding. Women of childbearing potential must have a negative serum or urine pregnancy test within 14 days prior to study entry and day of entry.
- History of chronic illnesses such as hypertension, coronary artery disease, arthritis, diabetes, hepatitis B or C virus infection, or gastrointestinal conditions that might interfere with drug absorption.
- Medical conditions that, in the opinion of the investigator, would interfere with the subject ability to participate in the protocol.
- Use of prohibited protocol-specified drugs, prescription, or over-the-counter (see Section 6.5.2 of the master protocol) within 14 days prior to study entry.
- Bleeding abnormality or other contraindication to lumbar puncture.
- Moderate or severe cognitive impairment by history or based on HIV Dementia Scale testing.
- Laboratory parameters documented within 21 days prior to study entry that would increase the risk for adverse events:
 - a. Hemoglobin < 12.5 g/dL for men; < 11.5 g/dL for women;
 - b. Platelet count < 100,000 platelets/mm³;
 - c. AST (SGOT) or ALT (SGPT) > 1.5 x the upper limit of normal (ULN);
 - d. Creatinine clearance < 70 ml/min;
 - e. Weight less than 50 kg;
 - f. Weight more than 20% over ideal body weight.

11. RECRUITMENT AND PROCEDURES PREPARATORY TO RESEARCH

If needed, the AVRC Outreach Department will develop recruitment tools, i.e., flyers/posters, and e-mails to community doctors which will be submitted to the IRB for review and approval prior to posting.

As this is a multicenter study, recruitment of HIV-1 infected subjects will be done through IRB-approved flyers posted in approved areas of the UCSD, University of Rochester (NY), and Erie County Medical Center (Buffalo, NY). All necessary precautions will be taken to ensure participants confidentiality. Participants will be informed in the informed consent document that their participation shall be confidential and their information shall be protected.

12. INFORMED CONSENT

This protocol and the informed consent document and any subsequent modifications will be reviewed and approved by the Institutional Review Board at each participating institution. Written informed consent will be obtained from the subject. Subjects who are unable to provide consent due to neurocognitive impairment or

other causes will not be enrolled. The informed consent will describe the purpose of the study, the procedures to be followed, and the risks and benefits of participation. A copy of the consent form will be given to the subject (or legal guardian). If the potential subject is still interested in participating, a clinic visit will be scheduled. The subject will be informed of the time that needs to be allotted for their first visit in which the informed consent will be administered.

The informed consent will describe the purpose of the study, the procedures to be followed, and the risks, and benefits of participation. This information will be explained to the study subject in a face-to-face setting by the individual consent the subject. Subjects will be encouraged to ask questions throughout the consent process and encouraged to discuss their participation with trusted advisors, such as family members, close friends, etc. Subjects will be allotted sufficient time to consider whether or not to participate in the research study. After allowing the potential subject time to read the informed consent the study staff and/or investigator will answer and address any questions or concerns the subject may have. Once all questions and concerns have been addressed and the subject wishes to participate, they will be asked to sign the informed consent.

Also, during the consent process, the Health Insurance Portability and Accountability Act (HIPAA) Authorization will addressed. A copy of the consent and HIPAA Authorization form as well as the Notice of Privacy Practices booklet will be given to the subject. A subject's bill of rights will also be given to the subject.

